10. APPENDICES

10.1. Data Handling

10.1.1. AE Start Date

10.1.1.1. Data Cleaning Process

Data entered through remote data capture (RDC) is under review at an ongoing basis. The data manager and clinical team send queries to the site to resolve inconsistency or missing data issues. The start date may be recorded as complete YYYY-MM, YYYY only, or completely missing.

10.1.1.2. Endpoints Impacted

The following variables will be impacted because the endpoints require AE start date in order to allocate each AE to a corresponding analysis interval:

- Proportion of subjects who develop at least one adverse event within 30 days after each vaccination visit.
- Proportion of subjects who develop at least one adverse event within 30 days after each vaccination visit after any vaccination visit.

Proportion of subjects who develop at least one adverse event during the vaccination phase.

Table 11. Analysis Interval

#	Analysis Interval	Interval Start date (inclusive)	Interval Stop (inclusive)
1	Within 30 days of vaccination 1	Vax 1 date	Vax 1 date +30 days
2	Within 30 days of vaccination 2	Vax 2 date	Vax 2 date +30 days
3	Within 30 days of vaccination 3	Vax 3 date	Vax 3 date + 30 days
4	Within 30 days of any vaccination	Each of above 3	Each of above 3
5	During the vaccination phase	Vax 1 date	1-month post-vaccination 3 blood sampling date (or the day the subject withdraw from the study for early withdrawal subjects)

It will also impact the medically attended AE, SAE, or newly diagnosed medical conditions, in which situations, similar data handling rule will be used.

10.1.1.3. Details on Data Handling

The general approach for data handling of the missing AE start date is to be conservative with regards to treatment emergence (or assume the worst for the sponsor).

10.1.1.3.1. Completely Missing

The AE start date will be imputed as the date of the first dose of study vaccination as long as the AE stop date is not prior to first vaccination date.

10.1.1.3.2. Partial Missing

Partial missing date with only month and year available:

1. If AE partial date indicates AE start date is prior to first dosing date, no imputation is needed since it can be slotted as ‘prior to vaccination phase’.

The protocols require to record all of the AE occurred after signing the informed consent document until the end of vaccination phase. For below example, this AE occurred prior to first vaccination based on year and month and can be slotted as an AE occurred prior to first injection with month and year. The date will not be imputed.

AE	AE Start Date	Date of Dose 1	Date of Dose 2	Date of Dose 3
Depression	2011-12	2012-01-05	2012-02-24	2012-06-14

If AE partial date indicates AE start date is after the vaccination phase, no imputation is needed either.

AE	AE Start Date	Date of Dose 1	Date of Dose 2	End of Vaccination Phase
Depression	2012-04	2012-01-05	2012-02-24	2012-03-14

2. If AE partial date could not determine if AE start date is prior to first dosing date, impute day to the first day of the month first and compare the imputed date with the first vaccination date and AE stop date.

- 2.1 If the imputed date is prior to the date of first dosing date and stop date is after first dosing date, **impute the date to the date of first dosing date**

AE	AE Start Date	AE Stop Date	Date of Dose 1	Date of Dose 2	Date of Dose 3
Common cold	2012-01	2012-02	2012-01-05	2012-03-01	2012-06-13

The partial date in above example will be imputed as ‘2012-01-05’, the date of the first vaccination date.

2.2 If the imputed date is after the first dosing date; **check the subsequent dosing date and AE stop date:**

A. If AE stop date is prior to the subsequent dosing date: stop here and use the first day of the month for imputation

AE	AE Start Date	AE Stop Date	Date of Dose 1	Date of Dose 2	Date of Dose 3
Common cold	2011-12	2011-12-03	2011-10-10	2011-12-05	2012-04-12

The partial date in above example will be imputed as ‘2011-12-01’, the first day of the month.

B. If AE stop date is after the subsequent dosing date: Compare the month of subsequent dose and the month of the AE

B1. If the AE start month is the same as the subsequent dose month: use the **subsequent dose date to impute the AE start day**

AE	AE Start Date	AE Stop Date	Date of Dose 1	Date of Dose 2	Date of Dose 3
Common cold	2012-01	2012-02-17	2011-11-22	2012-01-17	2012-05-09

The partial date in above example will be imputed as ‘2012-01-17’, the day of the second vaccination date.

B2. If the AE start month is not the same as the subsequent dose month: Stop here and keep the original **1st day of the month as imputed date.**

AE	AE Start Date	AE Stop Date	Date of Dose 1	Date of Dose 2	Date of Dose 3
Common cold	2012-03	2012-04	2011-10-10	2011-12-05	2012-04-12

The partial date in above example will be imputed as ‘2012-03-01’, the first day of the month.

Partial missing date with only year available:

The imputation approach will be the same as the missing day.

1. If AE partial date indicates AE start date is prior to first dosing date, **no imputation** is needed since it can be slotted as ‘prior to vaccination phase’.

AE	AE Start Date	Date of Dose 1	Date of Dose 2	Date of Dose 3
Depression	2011	2012-01-05	2012-02-24	2012-06-14

2. If AE partial date could not determine if AE start date is prior to first dosing date, impute day to January 1st of the year and compare the imputed AE start date with the earliest dosing date in the same calendar year and AE stop date.2.1. Compare the stop date with the earliest dosing date in that calendar year, if the stop date is earlier than the earliest dosing date in the same calendar year, the AE start date will remain the **first day of the calendar year**

AE	AE Start Date	AE Stop Date	Date of Dose 1	Date of Dose 2	Date of Dose 3
Common cold	2012	2012-01-12	2011-11-23	2012-02-08	2012-06-13

The partial date in above example will be imputed as ‘2012-01-01’, the first day of the year.

- 2.2. Compare the stop date with the earliest dosing date in that calendar year, if the stop date is later than the earliest dosing date in the same calendar year, the AE start date will be imputed as the **earliest dosing date in that calendar year**

AE	AE Start Date	AE Stop Date	Date of Dose 1	Date of Dose 2	Date of Dose 3
Common cold	2012	2012-06-12	2011-11-23	2012-02-08	2012-06-13

The partial date in above example will be imputed as ‘2012-02-08’, the earliest dosing date in calendar year 2012.

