7.6.3. Medically Attended Events and Newly Diagnosed Chronic Medical Conditions

MAEs and NDCMCs will be assessed throughout the vaccination period and up to Visit 8 (Month 12; 6-month follow-up visit) after the last study vaccination.

A medically attended event is defined as a nonserious AE that results in an evaluation at a medical facility.

A newly diagnosed chronic medical condition is defined as a disease or medical condition, not previously identified, that is expected to be persistent or otherwise long-lasting in its effects. This includes conditions that are undiagnosed prior to study entry (diagnosed while on the study) and that are not considered temporary conditions based upon the expected natural history of the condition.

7.6.4. Routine Medical Facility Visits, Elective Hospitalizations, and Routine Concomitant Medication Use Not Associated With Adverse Events

Routine visits to medical facilities and elective hospitalizations not associated with an AE, (ie, health care visits for preventive care, or for routine physical examinations), will not be collected. Non–AE-related concomitant medications other than vaccinations will not be collected. A study visit AE checklist will be used as a guide, completed at each scheduled study visit and telephone visit in Stage 1, and included in the source documentation. Please refer to the SRM for details.

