6.2.3. Safety Data Collected Through CRF

The relationship between (S)AEs and the investigational products (bivalent rLP2086 vaccine, saline, and HAV) will be characterized as related or not related as determined by investigators and as described in the protocol. The severity of AEs will be characterized as mild, moderate, and severe.

Adverse events with an onset prior to first vaccination will be excluded from AE analysis. These will be included in medical history analysis.

Adverse events will be categorized according to MedDRA.

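### The partial AE start-date rules have no branch for an ongoing event; read literally, they put one dated to the month or year of dose 1 before dose 1 and exclude it

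*SAP*

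**What the plan says.** SAP 10.1.1.1 expects incomplete dates: "The start date may be recorded as complete YYYY-MM, YYYY only, or completely missing". SAP 10.1.1.3 gives the principle: "The general approach for data handling of the missing AE start date is to be conservative with regards to treatment emergence".

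For a month-only start, SAP 10.1.1.3.2 assigns the first of the month and then tests it against the doses.
- Step 2.1 moves the date to dose 1: "If the imputed date is prior to the date of first dosing date and stop date is after first dosing date".
- Step 2.2 B leads to a move to dose 2 or 3, when the event and the dose share a month: "If AE stop date is after the subsequent dosing date".
- For a year-only start the provisional date is 1 January, and step 2.2 moves it to the first dose of that year "if the stop date is later than the earliest dosing date in the same calendar year".

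A completely missing start date is handled differently. SAP 10.1.1.3.1 assigns dose 1 "as long as the AE stop date is not prior to first vaccination date", which an ongoing event satisfies.

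SAP 6.2.3 fixes what a pre-dose date means: "Adverse events with an onset prior to first vaccination will be excluded from AE analysis". SAP 10.1.1.2 extends similar date handling to SAEs, medically attended events and newly diagnosed chronic medical conditions (NDCMCs). The protocol expects some events to have no end date: the visit procedures (for example 6.1.2) let the site record an event as still ongoing.

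**The concern.** Each branch that moves an event onto a dose date needs a stop date later than that dose. An ongoing event has none, so the only date the algorithm has given it is the provisional one. For the month or year of dose 1, that date is almost always before dose 1.

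The order of outcomes is then perverse. An ongoing event counts at dose 1 if nothing is known about its onset, but is excluded if the month is known. AEs are recorded from consent (Protocol 8.3), which the schedule places at Visit 1, so few AE-page events dated to the dose 1 month should truly precede dose 1.

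At stake are primary safety endpoints: the percentages with an AE, SAE, medically attended event or NDCMC. NDCMCs are the natural candidates, since the protocol defines them as a condition "that is expected to be persistent or otherwise long-lasting in its effects" (Protocol 7.6.3).

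**Working it through.** **Inputs.** Date rules: SAP 10.1.1.3.1 and 10.1.1.3.2. Exclusion: SAP 6.2.3. Intervals: SAP Tables 8 and 11. Dose windows: dose 2 at 42 to 70 days after dose 1, dose 3 at 105 to 126 days after dose 2 (Protocol 6.1.4, 6.1.6). Group sizes: Protocol 3.2.1 and 3.2.2.

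**Step 1: the SAP's own examples.** Coded literally, the rules reproduce all six imputed dates. The stop date was then removed and the provisional date left in place, since no branch moves it.

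| Step | Start | Relevant dose | SAP result | Same event, ongoing | Effect |
|---|---|---|---|---|---|
| 2.1 | 2012-01 | dose 1, 2012-01-05 | 2012-01-05 | 2012-01-01 | before dose 1; leaves every AE interval |
| 2.2 A | 2011-12 | dose 2, 2011-12-05 | 2011-12-01 | 2011-12-01 | none |
| 2.2 B1 | 2012-01 | dose 2, 2012-01-17 | 2012-01-17 | 2012-01-01 | leaves the dose 2 interval; stays in the vaccination phase |
| 2.2 B2 | 2012-03 | dose 3, 2012-04-12 | 2012-03-01 | 2012-03-01 | none |
| Year 2.1 | 2012 | dose 2, 2012-02-08 | 2012-01-01 | 2012-01-01 | none |
| Year 2.2 | 2012 | dose 2, 2012-02-08 | 2012-02-08 | 2012-01-01 | leaves the dose 2 interval; stays in the vaccination phase |

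In both year-only examples dose 1 was in 2011. If dose 1 itself were on 2012-02-08, an ongoing event dated 2012 would be set to 2012-01-01 and fully excluded.

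**Step 2: how often, given an ongoing event dated to the month or year of a dose.** Every dose 1 date in a 365-day year was combined with the protocol windows.
- Month of dose 1: excluded unless the dose was on the 1st, (365 − 12)/365 = 96.7%.
- Year of dose 1: excluded unless the dose was on 1 January, 364/365 = 99.7%.
- Month of dose 2: 96.7% leave the dose 2 interval. Of all cases, 76.4% fall in no 30-day interval and 20.3% move to the dose 1 interval. None leaves the vaccination phase, because the 1st is at least 42 − 30 = 12 days after dose 1.
- Month of dose 3: 96.7% fall in no 30-day interval, because the 1st is at least 105 − 30 = 75 days after dose 2. None leaves the vaccination phase.

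**Step 3: allowing for events that start in the next month.** Assume a month-only start, no stop date, and onset equally likely on days 0 to 30 after the dose. In a month of L days, the share of dose 1 events put before dose 1 is the sum over dose days d = 2 to L of (L − d + 1), divided by 31L, which equals (L − 1)/62. That is 29/62 = 46.8% for 30 days and 30/62 = 48.4% for 31 days. Simulation of 200,000 events gave 47.7%, with 42.8% of dose 2 and 47.4% of dose 3 events in no 30-day interval. These are shares of ongoing, month-dated events, not of all AEs.

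**Step 4: size of one event.** The selected dose has 33 × 2/3 = 22 sentinel and 132 × 2/3 = 88 expanded-phase children per age stratum, 110 in all: 1/110 = 0.9 points. With both strata combined at one dose, 1/220 = 0.45 points. In a dose group with sentinel children only, 1/22 = 4.5 points.

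**The case against.** The best defence is that the text is silent, not wrong. The branches that keep the provisional date (2.2 A, 2.2 B2 and year-only 2.1) also depend on a stop date, so nowhere does the SAP say that an ongoing event stays on day 1. SAP 10.1.1.3 states a conservative intent. SAP 10.1.1.4 says that when the dates give no clear indication the event can go to a 30-day interval, and that such events belong to the vaccination phase. An event confirmed as ongoing after a dose has plainly not stopped before it, so a sensible programmer might treat step 2.1 as met.

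It stands that pre-dose placement is a literal default and not a stated rule. A reader might infer that the SAP orders ongoing events to be placed before the dose; it does not. But 10.1.1.4 does not close the gap. It assigns no date, and the two branches it names both need a later stop date. Its reason, that a first-of-month or first-of-year date lies in the vaccination phase, fails for the month or year of dose 1, because Table 11 starts that phase at the dose 1 date.

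The defence is also right that partial dates are queried (SAP 10.1.1.1), and that dose 1 is followed by a visit at 7 to 10 days and a call at 25 to 35 days. Partial dates should therefore be rare where full loss is possible. Exclusion is not invisible either: SAP 6.2.3 moves pre-dose events to medical history, and SAP 8.2.5.2.1 lists all SAEs.

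**Conclusion.** The concern holds as a gap in the algorithm and a conflict within the SAP. Applied literally, the rules exclude an ongoing event dated to the month or year of dose 1 from every AE interval, unless dose 1 was on the provisional day. An ongoing event dated to the month of dose 2 or 3 loses that dose's 30-day interval, and usually every 30-day interval.

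Two stronger readings should be resisted.
- *Ongoing events at any dose drop out of the safety endpoints.* They do not. Dose 2 and dose 3 events stay in the vaccination phase and the Visit 1 to Visit 8 period, the intervals used for the between-group SAE, NDCMC and medically attended event comparisons (SAP 8.2.5.2.1, 8.2.5.2.2, 8.2.5.2.4).
- *Most NDCMCs are affected, or all the event percentages are materially lowered.* The definition makes ongoing NDCMCs likely, but the documents give no count of ongoing events or of partial dates. The number may be small after queries.

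Per lost event the size is about 0.9 points in a selected-dose stratum of 110. The 4.5-point figure applies only to a dose group of 22. The shares in the working rest on a program that leaves the provisional date in place and on doses within the protocol windows; those in step 3 also assume uniform onset over 0 to 30 days. The change is worth making because it is cheap and the affected categories may hold few events.

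**What to change.** In SAP 10.1.1.3.2:
- In steps 2.1, 2.2 B and year-only 2.2, make the condition: stop date is missing, ongoing, or on or after the dose date. This also settles a stop on the dose day, which the current wording leaves open.
- Apply 2.2 A and year-only 2.1 only when a known stop date is before the dose.
- Read a partial stop date as the last day of its month or year.

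With this change the three examples that shift when ongoing return to 2012-01-05, 2012-01-17 and 2012-02-08. Each then counts within 30 days of that dose and in the vaccination phase, in line with 10.1.1.3, 10.1.1.3.1 and 10.1.1.4. Immediate AEs are unaffected, because SAP 10.1.2.2.2 already keeps imputed dates out of that count.

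The cost is a few words in the appendix and one condition in the program. The downside is that a few events that truly began before a dose may be counted as post-vaccination, which is the direction the SAP says it prefers.

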10.1.1.4. Summary

With above imputation method, the most conservative approach was used. Therefore, if no apparent indication from the stop date and the part start date, the AE can be slotted to any of the primary endpoint analysis interval (within 30 days of vaccination). In addition, these events will be slotted to the vaccination phase, given the event is either imputes to the date of a vaccination day of the 1st day of the month (or year).

To be specific, 2.2.B1 (missing day) and case 2.2 (missing month and day) in [Section 10.1.1.3.2](#) will be allocated to **AE within 30 days after dose 2**.

10.1.1.5. Other Consideration

With imputed AE start date, the other variables might be impacted would be the AE duration. For MnB studies, the only duration to be summarized is the Reactogenicity data collected through e-Diary ([Section 10.1.4](#)). The duration of regular AE will not be summarized. However, each AE will be provided in the listing with a duration. If any AE with a missing or partial start date, the listing will not display the AE start day relative to the vaccination, nor the duration as the date is missing and the 2 variables cannot be derived with a missing date (ie, the raw data on the dates will be displayed).

10.1.2. AE Start Time

10.1.2.1. General Notes on Data Entry and Cleaning Process

The start time is to be recorded if the AE started on the same date of the vaccination. In addition, subjects are required to be observed for 30 minutes post-vaccination.

If any AE occurred on the vaccination day has a missing start time, a query will be sent to the site for confirmation of the time. If the site has confirmed that no additional data is available the start time will be recorded as unknown.

10.1.2.2. General Rule for Data Handling

In general, the AE start time will not be imputed.

10.1.2.2.1. AE Start Time Earlier Than Vaccination Time

If the AE start time is earlier than the first vaccination time, that AE will not be considered as an AE occurred during the vaccination phase, nor included as an AE within 30 days after the first vaccination.

If the AE start time is earlier than the second (or third) vaccination time, that AE will be included as an AE occurred during the vaccination phase. However, it will not be considered as an AE within 30 days after the second (or third) vaccination.

If AE start time is earlier than the vaccination time, the AE will not be considered as immediate because the immediate AE is defined as an AE occurred within 30 minutes **after** the vaccination.

10.1.2.2.2. AE Start Time Missing Due to Imputation of Partial AE Start Date

As mentioned in [Section 10.1.1.4](#), the AEs will be included in various AE analysis interval. The AEs imputed on the day of vaccination with the missing time will not be allocated to an interval that is prior to the vaccination.

However, these AEs will not be included as immediate AE because actual start time in the CRF would either include a specific time or ‘unknown’, if it is truly occurred on the same day of the vaccination based on protocol requirement. The imputation date in [Section 10.1.1](#) allows conservative calculation of AE in different analysis interval.

10.1.2.2.3. Unknown AE Start Time

Any AE with unknown AE start time will not be included in the immediate AE counting. As mentioned above, the site is required to observe the subjects for 30 minutes and record start time of any AE during the observation time. For any AE occurred on the same day of the vaccination day with an unknown start time, queries will be sent to site asking if the AE occurred within the observation period. If site confirmed the AE started during the observation period, the vaccination time will be entered so that this AE can be included as immediate AE. Otherwise, an estimated time is entered in the database.

Therefore, for any AEs with unknown time in the clean database, they are not included as immediate AEs. However, these AEs will be counted as within 30 days after that vaccination.

10.1.3. AE Events Collapsing

The AE log page is designed to collect one adverse event per record, therefore, no multiple AEs should be collapsed to one AE.

10.1.4. e-Diary Symptom Resolved Date

10.1.4.1. General Notes on Data Entry and Cleaning Process

According to protocol, investigators will be required to review the e-diary data online at frequent intervals to evaluate subject compliance and as part of the ongoing safety review. In addition, the investigator or designee must contact the parent/legally authorized representative in order to obtain stop dates for any reactions ongoing on the last day that the e-diary was completed.

The data manager and sponsor review the symptom resolved data at an ongoing basis to determine if any query is needed. Site is queried if the symptom resolve date is missing.

10.1.4.2. General Rule for Data Handling

10.1.4.2.1. Missing / Partial Symptom Resolved Date

If the symptom resolved date is completely missing or partially missing after the query, the dates will not be imputed. Therefore, in the summary table of ‘Duration of Local Reaction’ or ‘Duration of Systemic Events’, these events will be summarized as ‘Unknown’ duration.

[figure not shown]
In addition, the proportion of subjects with unknown duration among the subjects who reported such event will be summarized.

10.1.4.2.2. Calculation of Duration with Nonmissing Symptom Resolved Date

The symptom resolved date page can be filled in a scheduled visit which can have the symptom resolved page filled at unscheduled visit. In the programming handling, all of the CRF pages will be pooled together regardless the page origin. If the symptom resolved page indicated the symptom is continuing, the duration will be counted as ‘Unknown’.

First, the program logic will find all of the e-Diary events with the symptom present on the last day of the e-diary entry. It may not necessarily be day 7. For example, if subject’s e-diary is only transmitted until day 6, as long as the event is present on day 6, that event is picked for further consideration on the duration.

Second, the symptom resolved date from both data sources (planned page and unscheduled page) will be slotted to different interval based on the relative day to each vaccination as illustrated below:

Third, if the event occurred on the last day of the e-Diary entry after dose 1 has a resolved date in the first period (after dose 1 but prior to dose 2), the ending date for that event will be used to calculate the symptom duration. If the event occurred after the specific dose with a symptom resolved date not in the same period (ie, e-diary is after dose 1 but symptom resolved date is after dose 2 or after dose 3), the duration for that event will be assigned as ‘Unknown’. At the same time, a query is sent to the site for confirmation if the duration indeed lasted more than one period.

If the site confirmed that the event did span to more than one period, the duration will be calculated as segment. For example, if the first day of the e-diary is day 2 of dose 1 and the ending date is day 40 after dose 3, and each day of the e-diary entry is presented with the symptom on dose 2 and dose 3, the duration for that subject at each dose period will be calculated as:

After dose 1: (Dose 2 date -1) – (Dose 1 date) +1

After dose 2: (Dose 3 date -1) – (Dose 2 date) +1

After dose 3: (Symptom resolved date) – (Dose 3 date) +1

In addition, the subjects with duration spanned to multiple dosing period will be footnoted with overall duration longitudinally.

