For subjects experiencing any local reactions (or those with derived reaction presence in Table 4), the maximum duration (last day of reaction –first day of reaction +1) will be derived for each vaccination. Resolution of the event is the last day in which the event is recorded in the e-Diary or the date the event ends if it is unresolved during the subject diary-recording period, unless chronicity is established.

In summary, the following variables will be derived for local reaction:

1. Each local reaction on each day (up to day 7) after each vaccination.
2. Each local reaction on ‘any day 1-7’ after each vaccination and any vaccination.
3. Maximum severity of each local reaction on ‘any day 1-7’ after each vaccination and any vaccination.
4. Maximum duration of each local reaction after each vaccination.
5. Any local reaction on ‘any day 1-7’ after each vaccination and after any vaccination.

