8.2.5.1. Reactogenicity Data

The derived variables for the presence of each local reaction, each systemic event, fever, and use of antipyretic medication at each day and ‘any day 1-7’, and any local reaction and any systemic events at ‘any day 1-7’ will be summarized with number and proportion of subjects reporting such event, for each vaccination. The presence of each local reaction, each systemic event, fever, use of antipyretic medication, any local reaction, any systemic events will also be summarized for ‘any day 1-7’ after any vaccination similarly. The summaries will include 95% CIs. Clopper-Pearson’s method will be used to calculate the 95% CI.

The maximum severity of each local reaction, systemic events, and fever at ‘any day 1-7’ will be summarized with number and proportion of subjects reporting such maximum severity of the event, by each vaccination as well as ‘after any vaccination’. The summaries will include 95% Clopper-Pearson’s CI.

For local reactions and systemic events, including fever and use of antipyretic medication, the maximum duration of the event will be summarized for each vaccination. The number of unknown durations will also be summarized. The onset day for each local reaction and systemic event will also be summarized.

All of these summaries will be summarized according to the vaccine received. The safety population at each corresponding dose will be used for the analyses for each vaccination.

The data summaries will be descriptively presented by group.

Proportion differences (between rLP2086 dose groups and HAV/saline control group), associated 95% CIs and p-values will only be provided, by each vaccination and after any vaccination for the following endpoints:

- any local reactions (overall and by type of event) and any severe local reactions (only by type of event)
- any systemic events (overall and by type of event) and severe systemic events (only by type of event)
- any use of anti-pyretics
- any fever ($\geq 38.0^{\circ}\text{C}$) and also any temperature above or equal to 39.0-39.9, and 40 degrees centigrade.

P-values from the comparison and 95% exact CIs on the difference will be computed using the noninferiority procedure, using the standardized test statistic and $\gamma=0.000001$.

Also, the increasing severity and potentiation of local and systemic reactions across all 3 vaccinations will be summarized with number and proportion of subjects with such characteristics, along with 95% exact CI.

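### Diary reactions recorded as continuing, or lacking a full end date, get no numeric duration although a minimum is known, so the mean, upper tail and maximum of reported durations tend to be too low

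*SAP*

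**What the plan says.** SAP 6.2.2.1 defines duration as last day minus first day plus 1. It "will be derived for each vaccination. Resolution of the event is the last day in which the event is recorded in the e-Diary", or the later end date if the event was unresolved when the diary period closed. SAP 6.2.2.2 to 6.2.2.4 carry the same variable over to systemic events, fever and antipyretic use.

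SAP 10.1.4.2.2 sets out which events need an end date from the CRF: "First, the program logic will find all of the e-Diary events with the symptom present on the last day of the e-diary entry". It adds, on that last day, "It may not necessarily be day 7". The outcomes are then:

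- **Usable end date in the same dose period:** "if the event occurred on the last day of the e-Diary entry after dose 1 has a resolved date in the first period", that end date is used and the full duration is kept.
- **End date in a later dose period:** Unknown while the site is queried. Once confirmed, the duration is calculated by dose segment, with the overall duration in a footnote.
- **Still continuing:** "If the symptom resolved page indicated the symptom is continuing, the duration will be counted as" Unknown.
- **Missing or partial end date** (10.1.4.2.1): "If the symptom resolved date is completely missing or partially missing after the query, the dates will not be imputed", and the event is shown as Unknown.

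Unknowns are disclosed. SAP 8.2.5.1 states "The number of unknown durations will also be summarized", and 10.1.4.2.1 adds that "the proportion of subjects with unknown duration among the subjects who reported such event will be summarized".

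The default statistics for a continuous variable in SAP 8.1 are n, mean, median, standard deviation, minimum and maximum. No method for censored durations is given, and SAP 7.2.1 plans no sensitivity analysis for reactogenicity.

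**The concern.** Whether a reaction receives a number depends partly on how long it lasted. A reaction that has gone by the last diary entry always has a duration. One still present then has a duration only if someone later obtains its end date. A reaction recorded as continuing is right-censored: its end is not known, but it is known to have lasted at least from its first day to the last day it was seen. The SAP discards that lower bound.

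At stake is the description of persistence, chiefly the mean, the upper tail and the maximum. A reader who sees a maximum of so many days cannot tell that a reaction in the Unknown row had already lasted longer. The Unknown row also merges two different situations: a reaction known to be continuing, and one that has ended or may have ended but whose date was not recorded. According to SAP 10.1.1.5, reactogenicity duration is the only duration this study summarizes, so no other table fills the gap. For missing AE start dates SAP 10.1.1.3 deliberately takes the conservative side; here the omission leans the other way.

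**Working it through.** The plan states no expected duration, Unknown rate or bias, so there is no figure to reproduce. The check has three steps.

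**1. What is known about an Unknown reaction.** Inputs from the documents: the diary runs Day 1 to Day 7, with the vaccination day as Day 1 (SAP 6.2.2); duration = last day − first day + 1 (SAP 6.2.2.1); Visit 2 is 7–10 days after dose 1, and Visits 5 and 7 are 28–42 days after doses 2 and 3 (Schedule of Activities).

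- A reaction absent on a Day 7 entry ended by Day 6 at the latest, so its duration is at most 6 − 1 + 1 = 6 days.
- A reaction recorded as continuing at the earliest Visit 5 or 7 is present on Day 29. If it began between Day 1 and Day 7, it has lasted at least 29 − 7 + 1 = 23 to 29 − 1 + 1 = 29 days.
- At the earliest Visit 2 (Day 8) the same calculation gives at least 8 − 7 + 1 = 2 to 8 − 1 + 1 = 8 days.

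These bounds can be computed from data the study collects, and none enters the planned summary.

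**2. Direction.** Let u be the fraction Unknown, K the mean of known durations and U the true mean of the Unknowns.

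True mean = (1 − u)K + uU, and the relative understatement is 1 − K / true mean.

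The known mean is too low whenever U exceeds K. Because only reactions present on the last entry can be Unknown, that is the usual case, though not a certainty.

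**3. Illustrative size.** I simulated 400,000 reactions per scenario. All inputs are assumptions: onset on Day 1–3; geometric duration with mean 2 or 3 days; 2% or 5% of reactions instead lasting 7–40 days; 0% or 10% of diaries stopping before Day 7; and 10%, 30%, 50% or 100% of reactions present on the last entry becoming Unknown.

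| Of reactions present on last entry, share Unknown | Share of all reactions Unknown | Mean too low by | 95th percentile lower by | Median |
|---|---|---|---|---|
| 10% | 0.4–2.0% | 2–4% | 0–1 day | unchanged at 2 days |
| 30% | 1.3–5.8% | 7–11% | 1–3 days | unchanged at 2 days |
| 50% | 2.3–9.8% | 11–19% | 1–4 days | 2 to 1 day in some scenarios |
| 100% | 4.5–19.6% | 24–43% | 2–7 days | 2 to 1 day in some scenarios |

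One scenario as a check (short mean 2, 5% long, 30% Unknown, no early stops): u = 0.022, K = 2.747, U = 18.255. True mean = 0.978 × 2.747 + 0.022 × 18.255 = 3.09, and 1 − 2.747/3.09 = 11%.

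With 10% of diaries stopping early, about 13–37% of the Unknowns truly lasted 3 days or less. The mean was still too low in every scenario.

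**The case against.** The case for the SAP as written is substantial.

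- **Disclosure.** A reader might infer that these reactions are dropped from the duration tables. They are not: they form a reported category with a number and a proportion. This stands. A count, however, does not convey that a reaction lasted at least a given number of days.
- **Selection.** It is tempting to say that the longest reactions are removed, or that every Unknown outlasted the diary. Neither is supported. The trigger is lack of a usable end date. Long reactions with an end date are kept, and confirmed multi-dose reactions are calculated in segments. Since the last entry may precede Day 7, a short reaction in a diary that stopped early can also be Unknown.
- **Group comparison.** A reader might conclude that a difference in duration between vaccine and control is biased toward none. SAP 8.2.5.1 restricts differences, intervals and p-values to listed endpoints, and duration is not among them. How Unknowns would divide between arms is also not known.
- **Prevention.** Sites must contact parents for stop dates (Protocol 6.1 and 7.3) and are queried when one is missing (SAP 10.1.4.1). Redness or swelling above 14 caliper units is reported daily until it falls to that level or below (Protocol 7.4.1). Unknowns may therefore be few.
- **Table layout.** The shells are prepared separately, so exclusion of Unknowns from the mean and maximum is inferred. The inference is strong, because a duration that is not imputed has no value to enter.
- **Method.** Partial end dates are interval-censored, and Kaplan-Meier assumes non-informative censoring. This stands, and is why a censored-data summary should supplement the existing table and not replace it.

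**Conclusion.** The point holds in limited form. Under SAP 10.1.4.2, a reaction present on the last diary entry that is continuing, or whose end date stays missing or partial, has no numeric duration although a minimum is known. The mean, upper tail and maximum among known durations tend to be too low as a result; the median usually does not move.

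The size cannot be derived from the documents. It depends on the Unknown rate and on how long those reactions last, and neither is given. If few such reactions become Unknown, the assumptions above put the mean a few percent low. The larger figures in the table require half or more of the reactions present on the last entry to end as Unknown, which the site follow-up rules make unlikely.

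The effect is confined to the descriptive duration tables. The primary safety endpoints are percentages of subjects with reactions, including by severity, and are unaffected. This is a cheap improvement to reporting.

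**What to change.** In SAP 10.1.4.2 and 8.2.5.1:

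1. Split the Unknown category into reactions recorded as continuing and reactions whose end date is missing or partial, with a number and proportion for each.
2. Give each such reaction its minimum known duration, from its first day to the last date it is known to have been present (last diary day with the symptom, or the later contact at which it was still continuing).
3. Report the maximum as ≥ x days whenever the longest reaction is not known to have ended.
4. Keep the existing table and add a supplementary summary that treats continuing reactions as right-censored, for example Kaplan-Meier quartiles by group, and uses the known lower and upper bounds for partial end dates. State the censoring assumption in a footnote.

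The cost is a few lines of SAP text and a little programming. No new data are needed. Reported durations would become slightly less favorable.
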